The aim of this study is to determine the efficacy of Sancuso® (granisetron transdermal system) 3.1 mg/24 hours in improving symptoms of nausea and vomiting in patients with gastroparesis. This will be a prospective open-label study using Sancuso® to treat symptoms of nausea and/or vomiting in patients diagnosed with gastroparesis. Symptomatic patients with diabetic or idiopathic gastroparesis with nausea and/or vomiting will be enrolled. The Gastroparesis Cardinal Symptom Index Daily Diary (GCSI-DD) will be used to capture the severity of symptoms, including nausea and vomiting, at baseline for one week. Patients will then be treated with Sancuso[®]. Patients will continue to fill out the GCSI-DD on a daily basis while undergoing treatment with Sancuso® for two weeks. To determine if Sancuso® treatment helps improve symptoms of nausea and vomiting, the symptoms at baseline will be compared to symptoms after the first week and the second week of treatment. Thirty patients diagnosed with gastroparesis (approximately 15 with diabetic and 15 with idiopathic gastroparesis) will be treated on an open label basis with Sancuso®. The goal of this study is to demonstrate the efficacy of Sancuso® in treating nausea and/or vomiting in gastroparesis patients. Safety information will also be collected regarding any adverse effects. If the results are encouraging, as we expect them to be based on personal experience, a larger double blind study would be appropriate.

2) Protocol Title

Sancuso® in patients with nausea and/or vomiting from gastroparesis: An open label study.

3) IRB Review History

No prior IRB submission

4) Investigator

[name]; Temple University Hospital; GI Section; [name]; [contact]; Email: [contact]

5) Objectives

The aim of this study is determine the efficacy of Sancuso® in improving symptoms of nausea and vomiting in patients with gastroparesis.

The specific objectives of this study are to determine:

1) Determine the treatment response of Sancuso® in gastroparetic patients with nausea and/or vomiting.

2) Determine which specific symptoms of gastroparesis improve – nausea, vomiting, early satiety, abdominal distension, abdominal pain

3) To determine symptomatic responses in both diabetic and idiopathic gastroparesis

4) To determine the time course of symptom improvement (with Sancuso® for symptoms of gastroparesis;

The hypotheses to be tested include:

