- 1) Sancuso® improves symptoms of gastroparesis.
- 2) Symptoms of nausea and vomiting improve to a greater degree than abdominal pain.

3) The beneficial response of Sancuso® is seen in both diabetic and idiopathic gastroparesis.

4) The symptom reduction occurs on days 3 after starting treatment and continues throughout the treatment course.

Sancuso in patients with nausea and/or vomiting from gastroparesis: An open label study. Page 2

6) Background

Gastroparesis is a chronic, symptomatic disorder characterized by delayed gastric emptying in the absence of mechanical obstruction. There is a common association with longstanding diabetes, which comprises a majority of gastroparesis cases. Idiopathic gastroparesis represents another common form.

Symptoms of gastroparesis can be debilitating, causing frequent hospitalizations and diminished quality of life. Major symptoms of gastroparesis include nausea, early satiety, bloating and vomiting. Although symptoms have been difficult to associate with delayed gastric emptying, nausea and vomiting are two symptoms that appear to relate to gastric retention. Nausea is among the most commonly reported symptoms in gastroparesis. In a recent study by Anaparthy et al, nausea was one of the most prevalent symptoms, reported in 96% of patients undergoing evaluation for gastroparesis. Nausea and vomiting also have a major impact on the reduction in quality of life that occurs in gastroparesis.

Treatment of gastroparesis involves the use of prokinetic agents and antiemetic agents. Prokinetic agents are used to accelerate gastric emptying and include metoclopramide, a dopamine type 2 receptor antagonist. Antiemetic agents are used to reduce nausea and vomiting and include Compazine and Phenergan. Recently, the 5HT3 receptor antagonists, such as ondansetron and granisetron have been used.

Sancuso® is a topical formulation of the 5HT3 receptor antagonist granisetron. The patch provides treatment for prevention of chemotherapy induced nausea and vomiting; the patch can be left in place for 7 days. The PI has used this in some patients to help improve the symptoms of nausea and vomiting in patients with gastroparesis. It is particularly helpful in patients with symptoms, such as vomiting, which precludes oral ingestion of an antiemetic. In addition, it is helpful when repeated doses of oral ondansetron or oral granisetron are needed to control symptoms.

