The Gastroparesis Cardinal Symptom Index (GCSI) is a validated patient-reported outcome for gastroparesis using a two-week recall period. The nine symptom GCSI (nausea, vomiting, retching, stomach fullness, unable to finish a meal, feeling excessively full after meals, loss of appetite, bloating, belly visibly larger) is based on three subscales (postprandial fullness/early satiety, nausea/vomiting, and bloating). A larger symptom questionnaire, the Patient Assessment of GI Symptoms (PAGI-SYM) includes the 9 symptoms in the GCIS, and additional symptoms of gastroesophageal reflux disease and functional dyspepsia. A daily diary form of the GCSI has been developed (GCSI-DD) includes symptoms relevant to patients with gastroparesis, captures daily variability of those symptoms and has psychometric properties consistent with a good patient-reported outcome endpoint for gastroparesis clinical trials. Each of these questionnaires, the PAGI-SYM, the GCSI, and the GCSI-DD are in the public domain for use by investigators and physicians.

7) Setting of the Human Research

Patients are seen for clinical care by [name] in the third floor of the Ambulatory Care Center of Temple University Hospital. For patients with refractory symptoms of nausea and/or vomiting from their gastroparesis, which comprise many of [name] patients, other offlabel treatment options are discussed including the use of tricyclic antidepressant agents as symptom modulators, botulinum toxin injection into the pylorus, gastric electric stimulation, and more recently the use of Sancuso® (granisetron transdermal system). If it is elected to proceed with Sancuso® for their clinical care, then the patients will be approached about participating in this open label study which will be recording their response to treatment.

The clinical nurse practitioner, [name], has an office in the GI Section where she will see patients in this study. Patients will be seen in five visits for this study.

Sancuso in patients with nausea and/or vomiting from gastroparesis: An open label study. Page 3

8) Resources Available to Conduct the Human Research

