Visit 4: Patients will be seen after the second one week of treatment. The GCSI daily diaries will be collected. The therapeutic response of the patients will be enquired using the simple Clinical Patient Grading Assessment Scale (CPGAS). Patients will fill out the Patient Assessment of GI Symptoms (PAGI-SYM), SF-36, HAD questionnaire, a modified McGill Pain

inventory, and a symptom side effect questionnaire. Patients will stop treatment with Sancuso® at this time, and be followed for an additional week of treatment off medication. Patients will continue to fill out the GCSI-DD on a daily basis and not take any 5-HT3 receptor antagonist. A follow up appointment in one week will be scheduled.

Visit 5: Patients will be seen after one week after cessation of treatment. The GCSI daily diaries will be collected. Patients will fill out the symptom side effect questionnaire. After this visit, the study period is over and the patient returns to clinical care.

f) Study Endpoints

Primary and Secondary Endpoints:

Primary:	Nausea and Vomiting severity scores using the GCSI-DD
Secondary:	Total Gastrointestinal Cardinal Symptom Index
-	Clinical Patient Grading Assessment Scale (CPGAS)

Patients will fill out daily information of their symptoms of gastroparesis using the Gastroparesis Cardinal Symptom Index Daily Diary (GCSI-DD). The Gastroparesis Cardinal Symptom Index (GCSI) is a validated patient-reported outcome for gastroparesis daily recording of symptoms. Several symptoms of gastroparesis including nausea, vomiting, retching, stomach fullness, unable to finish a meal, feeling excessively full after meals, bloating, belly visibly larger will be monitored. This is used in clinical practice and will be performed in this project.

For this study, the therapeutic response of the patients will also be enquired using the simple Clinical Patient Grading Assessment Scale (CPGAS). Patients will be asked if they improved, stayed the same, or worsened with Sancuso® treatment. The clinical response of their gastroparesis symptoms to Sancuso treatment with gradations from (+7) = completely better; (0) = no change, and (-7) = very considerably worse. Responders are defined as those with score of >0 and non-responders with score of \leq 0 by CPGAS. Patients will be asked if they experienced any side effects with Sancuso® treatment and to describe any side effects. Other than your GI symptoms, how have you been feeling?

Adverse events will be recorded.

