g) Procedures Involved in the Human Research

This will be an open label study of patients with gastroparesis. The study period will be approximately four weeks.

Patients meeting the inclusion criteria will be asked to participate and sign informed consent. Baseline information will be collected including History and Physical Examination, EKG, routine clinical blood work. The history will include prior 5-HT3 receptor antagonist treatment and the patient's response. Patients will fill out baseline questionnaires including the Patient Assessment of GI Symptoms (PAGI-SYM) for assessment of GI symptoms over the past 2 weeks, SF-36 to assess their quality of life, HAD questionnaire to assess for symptoms of anxiety and depression, and a modified McGill Pain inventory to assess for abdominal pain.

Patients will be treated with Sancuso® for two weeks (one patch every 7 days), being seen after each week. A copy of the package insert for Sancuso in in the appendix. Symptoms will be followed on a daily basis using the GCSI-DD

At the study visits, the GCSI daily diaries will be collected. At each of these visits, patients will fill out the Patient Assessment of GI Symptoms (PAGI-SYM), SF-36, HAD questionnaire, a modified McGill Pain inventory, and a symptom side effect questionnaire.

After the two weeks of active treatment, the patient will be followed for a further week off treatment, for a study period of 4 weeks (one week baseline off treatment, two weeks treatment with Sancuso®, then one week off treatment).

Sancuso in patients with nausea and/or vomiting from gastroparesis: An open label study. Page 6

Adverse event reporting

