Descriptive analysis of the outcome variables will be constructed. Statistical analysis will be performed using SPSS. This study is designed to test the hypothesis that Sancuso® treatment provides improvement of gastroparetic symptoms. We will compare the absolute GCSI symptom scores before and after treatment using ANOVA for repeated measures. The symptom score improvement will be tested between the two treatment groups (diabetic and idiopathic gastroparesis) using ANOVA for repeated measures on ranks. Linear regression will be used to identify potential predictors of a beneficial symptomatic response to treatment.

Sample Size Determination

In a gastroparesis study at our institution with similar inclusion criteria, the average GCSI of 16 patients was 34.8 with standard deviation of 4.6. In a previous study at our institution, the absolute magnitude of symptom improvement for open label botulinum toxin was 38% (Miller 2002). The sample size in this study is calculated to show a benefit of Sancuso® by at least 30% reduction in the GCSI score. Assuming a standard deviation of 5 in the GCSI reduction of symptoms and with an α = .05 and β = .80, fifteen patients will be needed. We will recruit 15 diabetic patients and 15 idiopathic patients to enter this study to give adequate power to address the primary outcome variable - symptom response.

j) Confidentiality

Private health information (PHI) as defined by HIPAA will be collected as part of the research. These include: name, birthdate, telephone number, medical record number. All data will be kept confidential. Data will be entered into an Excel spreadsheet in an encrypted password protected computer accessible only be the study coordinator and the PI. The data will be deidentified.

k) Provisions to Monitor the Data to Ensure the Safety of subjects

This study involves minimal risk to the subjects. Patients will be monitored during the study in weekly study visits. The Sancuso® patch is being used to try to help reduce their symptoms of nausea and/or vomiting. The study is to allow recording of the response to treatment. All data will be kept confidential. Data will be entered into an Excel spreadsheet in an encrypted password protected computer accessible only be the study coordinator and the PI.

I) Withdrawal of Subjects

Patients have the option to not participate. Patients may elect at any time to stop treatment with Sancuso®.

11) Risks to Subjects

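### Objective 2 and hypothesis 2 ask which symptoms improve and which improve more, but the plan names no test that symptoms change by different amounts and no analysis of abdominal pain

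*Combined protocol and SAP*

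**What the plan says.** Section 5 (Objectives), specific objective 2, reads: "Determine which specific symptoms of gastroparesis improve". It names five: nausea, vomiting, abdominal pain, abdominal distension and early satiety. Hypothesis 2 in the same section is comparative: "Symptoms of nausea and vomiting improve to a greater degree than abdominal pain".

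Section 10(i), Data Analysis, gives one sentence that bears on these: "We will compare the absolute GCSI symptom scores before and after treatment using ANOVA for repeated measures". It does not say whether this is done per item, per subscale or on the total. It gives no rule for multiple symptoms and no comparison of one symptom's change with another's. The two other named analyses, diabetic against idiopathic patients and a regression for predictors of response, do not compare symptoms. The 25% improvement criterion under Outcome measures is set for nausea only.

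Section 6 (Background) lists the items of "The nine symptom GCSI", which "is based on three subscales (postprandial fullness/early satiety, nausea/vomiting, and bloating"; none is abdominal pain. Section 10(f) lists eight diary symptoms, beginning "Several symptoms of gastroparesis including nausea, vomiting, retching, stomach fullness, unable to finish a meal"; pain is not among them. Pain is collected separately, by "a modified McGill Pain inventory to assess for abdominal pain" (section 10(g)), for which no analysis is stated.

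**The concern.** Hypothesis 2 is a claim about a difference between symptoms. A before/after test answers a different question: whether a given score changed. If the test is run symptom by symptom, the natural reading is to list those that reach significance and those that do not. One significant result and one non-significant result do not show that two symptoms differ. When all symptoms move together, as they may in an open-label before/after study, sampling error alone can split the list. A split with nausea and vomiting on one side would look like the selectivity that hypothesis 2 predicts.

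If the ANOVA is run only on the total score, objective 2 has no analysis at all. For abdominal pain the GCSI comparison does not apply on either reading, so hypothesis 2 cannot be tested by the plan as written.

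**Working it through.** **Inputs from the plan.** Five symptoms (objective 2); 30 patients in one arm; α = .05, taken as two-sided because sidedness is not stated. A paired t test with 29 degrees of freedom stands in for the repeated-measures ANOVA; with two time points they are the same test.

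**Inputs assumed.** The plan gives no symptom-level effect, SD or correlation. I use an equal true improvement d of 0.3, 0.5 or 0.8 (in SDs of the change score), correlation between symptom changes from 0 to 0.7, and no dropout. A symptom counts as improved if significant in the favourable direction.

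**The plan's own planning figure.** The target is 0.30 × 34.8 = 10.44 points; with SD 5, d = 10.44/5 = 2.09. The paired normal formula gives ((1.96 + 0.84) × 5/10.44)² = 1.8, so 2 patients; a paired t calculation gives 4 to 5. The stated 15 is not reproduced and exceeds what its inputs require. It concerns the GCSI score as a whole, so it does not give power for a single symptom.

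**Step 1: power for one symptom, n = 30** (noncentral t, noncentrality d√30): 36% at d = 0.3, 75% at d = 0.5, 99% at d = 0.8.

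**Step 2: chance of a split list when all five improve equally.** For independent symptoms this is 1 − p⁵ − (1 − p)⁵, where p is the power:
- d = 0.3: 1 − 0.355⁵ − 0.645⁵ = 1 − 0.006 − 0.112 = 0.88
- d = 0.5: 1 − 0.754⁵ − 0.246⁵ = 1 − 0.244 − 0.001 = 0.76
- d = 0.8: 1 − 0.9885⁵ − 0.0115⁵ = 1 − 0.944 − 0.000 = 0.06

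Simulation of correlated paired t tests (40,000 trials) agrees at correlation 0 and gives the other end of the range:

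| Equal improvement in all five | Split list, correlation 0 | Split list, correlation 0.7 |
|---|---|---|
| 0.3 SD | 88% | 49% |
| 0.5 SD | 76% | 42% |
| 0.8 SD | 6% | 4% |

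All symptoms change equally here, so every split is a chance pattern. A valid 5% test of differences between symptoms would claim selectivity in 5% of such trials.

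**Step 3: nothing changes.** For independent symptoms, at least one false improvement has probability 1 − 0.975⁵ = 11.9%. By simulation it is 12%, 11%, 9% and 8% at correlation 0, 0.3, 0.5 and 0.7.

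**Step 4: what adjusting p-values would do.** With no true change, Holm lowers false improvements from 12% to 2.5% (correlation 0) or from 9% to 2% (correlation 0.5). With two of five symptoms truly improved by 0.5 SD at correlation 0.5, it raises the chance of missing at least one from 38% to 64%. If a non-specific improvement of 0.3 SD is added to all five symptoms in that case, at least one of the other three is called improved in 60% of trials unadjusted and still in 39% with Holm.

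**The case against.** Several points on the other side stand.

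- **The sorting rule is inferred.** The plan states no p < .05 rule for classifying symptoms, and it also plans descriptive analysis. The rates above show what follows if the list is read from separate tests, not what the plan commits to.
- **The results depend on the assumed effect.** At 0.8 SD the split-list problem nearly vanishes, and the only planning effect in the document is larger still, though on the total score.
- **These symptoms are mostly not lead outcomes.** Nausea and vomiting are primary; total GCSI and the CPGAS are secondary. The opening summary says encouraging results would justify a larger double-blind trial. It does not say a symptom list would carry into it.
- **The diary form is not in the text.** The eight symptoms in section 10(f) are given as examples, so the form could hold a pain item. Data Analysis would still need to name it.

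A reader might infer more than the documents support:

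- **That the list is likely to be wrong in both directions.** False improvements dominate when nothing changes and misses when effects are moderate; these are different situations. With two of five symptoms truly improved, both errors fell in the same list in at most about 6% of simulated trials.
- **That the error rate is 37%.** That is 1 − 0.95⁹: nine independent items, counting worsening as well as improvement. Objective 2 names five symptoms and asks about improvement.
- **That a multiplicity adjustment is the cure.** Step 4 shows that it trades one error for the other and leaves shared open-label change largely in place.

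**Conclusion.** The concern holds as a gap between question and analysis. Objective 2 and hypothesis 2 need a comparison between symptoms; the plan offers only a before/after comparison of GCSI scores and states no analysis for abdominal pain. Followed as written, any statement that some symptoms respond more than others would rest on separate tests.

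The size depends on symptom-level effects that the plan does not give: the risk of a chance split is substantial for equal improvements of 0.3 to 0.5 SD and small at 0.8 SD. The false-improvement rate if nothing changes is modest. The primary nausea and vomiting comparison is not called into question by this point.

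**What to change.** Add to Data Analysis:

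1. Test differences between symptoms directly, within patients: a symptom-by-time interaction for the GCSI-DD symptoms and, for hypothesis 2, a paired contrast of the change in nausea/vomiting against the change in a named abdominal pain score. State how the scales are made comparable. Dividing by baseline SD is debatable, because eligibility requires at least moderate nausea and vomiting, which may narrow their baseline spread. Claim that some symptoms improve more than others only from these tests.
2. Report every symptom's mean change with a 95% confidence interval. Label single-symptom results other than the primary nausea/vomiting scores exploratory, and do not read non-significance as no improvement.

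Holm adjustment of single-symptom tests is optional, for the reason in step 4.

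The cost is a few sentences and slightly more analysis; nausea, vomiting and pain measurements are already planned. A selectivity claim becomes harder to make. For example, at correlation 0.5 the difference between two standardised changes has SD √(2 × (1 − 0.5)) = 1, so a true difference of 0.5 SD would have about 75% power with 30 patients. The direct test cancels open-label improvement shared equally across symptoms. It does not remove unequal non-specific change, and patients are selected on nausea and vomiting but not on pain, so that limit should be stated with the result.

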The Principal Investigator will be responsible for the reporting and submission of serious (expected or unexpected) adverse events that occur during the conduct of this study to FDA on a MedWatch 3500a form. Additionally, the Principal Investigator will be responsible for providing the required study update reports to the Institutional Review Board (IRB). The Principal Investigator will also provide ProStrakan with a copy of the MedWatch 3500a completed for all serious adverse event reports. The information includes the investigator's assessment of causality. This information will be sent to the company within 10 days of receipt of the adverse event report by the Investigator. A copy of the completed MedWatch 3500a form submitted to FDA will be sent to [contact]. The company will enter all safety information in the Global Safety Database along with the investigator's assessment of relationship of the event to the study medication. Any follow up information will also be sent to the company within 10 days of receipt of the adverse of the adverse of the study medication. Any follow up information will also be sent to the company within 10 days of receipt of the information by the Investigator on a completed MedWatch 3500a form.

h) Data and Specimen Banking

Data will be stored on encrypted password-protected computer using a Microsoft Excel data base. No specimens will be obtained.

i) Data Management

Data will be entered into an Excel spreadsheet in an encrypted password protected computer accessible only to the study coordinator and the PI.

Descriptive analysis of the outcome variables will be constructed using Excel and SPSS.

Outcome measures

The primary outcome measures in this study are the GCSI-DD nausea/vomiting symptom scores. The secondary outcome measures are Total Gastrointestinal Cardinal Symptom Index and Clinical Patient Grading Assessment Scale (CPGAS). The percent of patients treated with Sancuso® that have improved symptoms of nausea, vomiting will be calculated both as a positive score on the CPGAS as well as a 25% improvement in the nausea score compared to baseline.

Data Analysis

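### The power claim for the primary outcome rests on the GCSI score, not on the nausea/vomiting scores declared primary, and no single score or contrast is named to decide that primary.

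*Combined protocol and SAP*

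**What the plan says.** **Primary outcome.** Section 10(f) lists "Nausea and Vomiting severity scores using the GCSI-DD". Section 10(i), Outcome measures, states: "The primary outcome measures in this study are the GCSI-DD nausea/vomiting symptom scores". Both are plural. Both sections make the total index and the CPGAS secondary. Section 6 describes a nausea/vomiting subscale of the GCSI, but no section names it as the primary. Section 10(i) also sets a responder threshold on nausea alone: "a 25% improvement in the nausea score compared to baseline".

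**Timing.** The opening summary compares baseline with the first and the second treatment week and makes neither decisive.

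**Analysis.** Under Data Analysis in section 10(i), the hypothesis is that Sancuso "treatment provides improvement of gastroparetic symptoms", and the method is: "We will compare the absolute GCSI symptom scores before and after treatment using ANOVA for repeated measures".

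**Sample size.** The same section reports that "the average GCSI of 16 patients was 34.8 with standard deviation of 4.6", aims to show a benefit "by at least 30% reduction in the GCSI score", assumes an SD of 5 for the reduction, and arrives at fifteen patients. It recruits 15 diabetic and 15 idiopathic patients and says this gives adequate power for the primary outcome variable, there called symptom response.

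**The concern.** There are two linked gaps. First, the power statement is made for the primary outcome but calculated on another score. The documents contain no figure from which power for a nausea/vomiting score could be calculated, so the claim has no support as written.

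Second, the text does not say which score, which week or which contrast decides the primary. That choice could be made after the data are seen, and testing more than one candidate at .05 raises the chance of a false positive. This matters because the opening summary sets a goal of demonstrating efficacy and makes a larger double-blind study depend on encouraging results.

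**Working it through.** **1. The plan's own figure.** Inputs from Sample Size Determination: mean 34.8, reduction 30%, SD of reduction 5, α = .05, and β = .80, read here as power 0.80. Sidedness is not stated; two-sided is assumed.

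- Target change: 0.30 × 34.8 = 10.44 points. Standardized: 10.44 / 5 = 2.09 SD.
- Normal approximation for a paired change: n = [5 × (1.960 + 0.842) / 10.44]² = 1.8, so 2 patients.
- Paired t-test (noncentral t): 5 patients, with 93% power.
- At 15 patients, power on these inputs exceeds 99.9%.

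So 15 does not follow from the stated inputs. The discrepancy is towards more patients than the inputs require, so it is not evidence of a shortfall on the GCSI score.

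**2. Whether this carries over to the primary.** The calculation concerns the GCSI score; the primary is the GCSI-DD nausea/vomiting scores. That 34.8 is the nine-item total is an inference, since the paragraph does not say total. The gap does not depend on it: whatever 34.8 measures, it is not identified as a nausea/vomiting score. The only nausea figure is the 25% threshold, which classifies individual patients and is not a target mean change. No power for the primary can be calculated in score units.

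**3. What the planned size detects.** Let d = mean change / SD of change. For one two-sided .05 paired t-test, power is the probability that a noncentral t with n − 1 degrees of freedom and noncentrality d√n exceeds the critical value. The values of d in the first three rows are assumed, not taken from the documents.

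| d | n = 15 | n = 30 |
|---|---|---|
| 0.3 | 19% | 36% |
| 0.5 | 44% | 75% |
| 0.8 | 82% | 99% |
| d giving 80% power | 0.78 | 0.53 |

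Both columns are needed: the plan says fifteen patients suffice and recruits 15 per etiology, 30 in all.

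**4. False-positive rate by decision rule.** Null simulation with n = 30, baseline and two treatment weeks, and each test at two-sided .05. Assumed correlations are 0.3–0.7 between the two scores and 0.5–0.8 between the week-1 and week-2 changes.

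- One repeated-measures ANOVA on one subscale score: 4.9–5.2% with equal correlations between weeks; 4.6–5.0% with unequal correlations and a Greenhouse-Geisser correction; 5.5–6.7% with unequal correlations and no correction.
- Two scores, one ANOVA each: 8.4–9.5% with equal correlations; 8.2–9.4% with unequal correlations and correction; 10.2–12.8% with unequal correlations and no correction.
- One score, either treatment week able to count: 7.8–9.4%.

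As a check, two independent tests would give 1 − 0.95² = 9.75%. The fourth, off-treatment diary week was not simulated.

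**The case against.** The ambiguity is narrower than it first looks. Section 10(i) uses the same slash label that section 6 gives to the subscale, and the plural may only reflect a score recorded daily. The visit schedule speaks of GCSI daily diaries, so the GCSI symptom scores in the analysis paragraph could include the diary primary. A repeated-measures ANOVA has one overall test of time, so a decisive week is not strictly required. The study is also a small, single-arm, open-label precursor to a blinded trial.

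Much of this stands. One ANOVA on one subscale score is a legitimate plan with close to nominal error. But no section states that reading. Section 10(f) names nausea and vomiting as words joined by a conjunction, section 10(i) uses a separate nausea score, and the weeks entering the ANOVA are not listed. None of these readings repairs the power claim.

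A reader might go further in two ways that the documents do not support. One is that the trial is underpowered. The 0.3–0.8 SD range is assumed, and at its upper end power with 30 patients is 99%. The other is a false-positive rate of about 13–17%. That requires either score at either week to count on its own, which is planned nowhere.

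**Conclusion.** The power claim is unsupported as written: it is calculated at 2.09 SD on the GCSI score and asserted for a primary on which the documents give no mean, SD or target mean change. The correct statement is that power for the declared primary is not shown, not that it is low.

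The lack of one deciding score and contrast is a smaller, real gap. Its cost ranges from essentially none (about 5%, one ANOVA on one score with a sphericity correction or equal correlations) to about 8–10% if two scores, or two weeks, can each count at .05. Those rates rest on the assumed correlations, and the two-ANOVA case also needs a correction or equal correlations to stay in that range.

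The wording should be corrected. Doing so leaves placebo response and regression to the mean untouched in a single-arm before-after comparison.

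**What to change.** - In section 10(f) and in the Outcome measures, Data Analysis and Sample Size paragraphs of section 10(i), use one identical primary: one score (for example the weekly mean GCSI-DD nausea/vomiting subscale) and one deciding test in all patients.
- The test can be the planned repeated-measures ANOVA over stated weeks with a sphericity correction, or one pre-stated contrast of baseline with a named treatment week. The documents give no reason to prefer one week, so this is the investigator's choice, to be made before data are seen.
- Make the other items, weeks and etiology subsets secondary. If several primaries are kept, state a testing order or an adjustment. Splitting α over two tests raises the change detectable at 80% power with 30 patients from 0.53 to 0.59 SD.
- Replace the power claim with a statement that the calculation concerns the GCSI score and does not show power for the primary. Add that one two-sided .05 paired test has 80% power for a mean change of 0.53 SD with 30 patients and 0.78 SD with 15 (one etiology).

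The cost is wording only, with no extra patients or visits. The other items and weeks lose primary status, and the stated power becomes less favourable. Re-sizing the study on the primary score would be a different step: it needs figures that the documents lack and could change the number of patients.
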